7.5.1.7 Week 12 (\pm 7 days)

[figure not shown]
The following procedures will be performed and all observations will be recorded in the eCRF:

- Review of concomitant medications.
- Update transfusion history status.
- A targeted physical examination will be performed, including body weight and measurement of spleen by palpation ([Section 8.2.3](#)).
- Vital signs (blood pressure, heart rate, respiratory rate and body temperature) to be performed in a sitting position after 5 minutes of rest.
- Blood sampling for serum chemistry tests, hematology, and optional coagulation (PT, PTT, or INR) (see [Appendix III](#)).
- 12-lead ECG performed in the recumbent position after 5 minutes of rest.
- Determination of ECOG performance status (see [Appendix IV](#)).
- Complete FACT-Lym version 4 ([Appendix VII](#)) and FACIT-Fatigue Subscale (prior to examination) ([Appendix VIII](#))
- MRU in the past month:
 - Number and duration of each hospitalization.
 - Number of emergency room visits.
 - Number of urgent care visits.
 - Number of additional general practitioner and specialist office visits.
 - Number of transfusions and transfusion dependency status.
 - Splenectomy or splenic irradiation.
- Document new (changed) or ongoing dose information for INC424. Dose changes that are necessary between study visits will be communicated immediately and directly to the patient by telephone; the communication will be documented in the source documents.
- Drug accountability assessment (see [Section 6.5.4](#)).
- Assess patient compliance
- Record adverse events.
- Study drug for the next 84 days (plus overage) will be dispensed along with dosing instructions.
- Patients will be instructed to call the investigator or designated research staff if they experience any unexpected and unfavorable signs and/or symptoms. These adverse events will be recorded on the eCRF. Patients will be reminded to bring the study drug to the clinic with them.

7.5.1.8 Week 12 through Week 24

Patients will self-administer INC424 twice daily as instructed, morning and evening, in an outpatient setting. Patients will call the Investigator or designated research staff if they experience any unexpected and unfavorable signs and/or symptoms.

Those patients who underwent dose modifications at the Week 12 (Month 3) visit must return to the clinic as follows:

- Patients experiencing hematologic adverse events - following laboratory draws as outlined in [Section 6.2.2](#).
- Patients who underwent dose escalation at week 12 (Month 3) should return to the clinic for serum chemistries and hematology assessments.

7.5.1.9 Week 24 (\pm 7 days)

The following procedures will be performed and all observations will be recorded in the eCRF:

- Review of concomitant medications.
- Update transfusion history status.
- A complete physical examination will be performed, including body weight and measurement of spleen by palpation ([Section 8.2.3](#)).
- Vital signs (blood pressure, heart rate, respiratory rate and body temperature) to be performed in a sitting position after 5 minutes of rest.
- Blood sampling for serum chemistry tests, hematology, and optional coagulation (PT, PTT, or INR) (see [Appendix III](#)).
- Determination of ECOG performance status (see [Appendix IV](#)).
- Complete FACT-Lym version ([Appendix VII](#)) and FACIT-Fatigue Subscale (prior to examination) ([Appendix VIII](#)).
- Medical resource utilization in the past month:
 - Number and duration of each hospitalization.
 - Number of emergency room visits.
 - Number of urgent care visits.
 - Number of additional general practitioner and specialist office visits.
 - Number of transfusions and transfusion dependency status.
 - Splenectomy or splenic irradiation.
- Drug accountability assessment (see [Section 6.5.4](#)).
- Record adverse events.
- Assess patient compliance.
- Document new (changed) OR ongoing dose information for INC424. Dose changes that are necessary between study visits will be communicated immediately and directly to the patient by telephone; the communication will be documented in the source documents.
- INC424 for the next 84 days (plus overage) will be dispensed along with dosing instructions.
- Patients will be instructed to call the investigator or designated research staff if they experience any unexpected and unfavorable signs and/or symptoms. Patients will be reminded to bring the study drug to the clinic with them.

7.5.1.10 Week 24 through Week 36

Patients will self-administer INC424 BID as instructed, morning and evening in an outpatient setting. Patients will call the investigator or designated research staff if they experience any unexpected and unfavorable signs and/or symptoms.

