3.3.4 Medical resource utilization (MRU)

[figure not shown]
Medical resource utilization (MRU) will be assessed as follows:

- Frequency and duration of hospitalization from Baseline up to week 48 of therapy
- Frequency of emergency room visits from Baseline up to week 48 of therapy.
- Frequency of general practitioner, specialist, and urgent care visits from Baseline up to week 48 of therapy.
- Number of transfusions and transfusion dependency status end of study.
- Splenectomy and use of splenic irradiation.
- Changes in use of concomitant medications for MPN symptom management ([Appendix IX](#)).

4 Study design

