Day of visit		-28 to -1	-7 to -1	Day 1	Day 28	Day 56	Day 84	Day 168	Day 252	Day 336				
Vital signs (D)	7.4/8.2.4	X	X		X	X	X	X	X	X	X	X	X	X
Height (D)	7.3/8.2.5	X												
Weight (D)	7.4/8.2.5	X	X		X	X	X	X	X	X	X	X	X	X
Full neurologic and cardiac assessment for fедратиниб pretreated patients (S)	7.3/8.2.6	X												
Measurement of spleen by palpation (D) (See Section 8.3.1.1)	7.4	X	X		X	X	X	X	X	X	X	X	X	X
ECOG performance status (D)	7.4	X	X		X	X	X	X	X	X	X	X	X	
12-lead ECG (D) (See Section 7)	7.4	X	X		X		X			X				
Adverse events (D)	7.4/8.2.1	X	X	X	X	X	X	X	X	X	X	X	X	X
Quality of Life	7.4/8.3.2													
FACT-Lym version 4 (D)	7.4/8.3.2		X		X		X	X		X				
FACIT-Fatigue Subscale (D)	7.4/8.3.2		X		X		X	X		X				
Medical resource utilization (D)	3.3.4/7.4		X		X	X	X	X	X	X				
Dispense Investigational Product (D)	7.4			X	X	X	X	X	X	X	X			
Drug Accountability Assessment (D)	6.5.4/7.4				X	X	X	X	X	X	X	X	X	
Assess Investigational Product Compliance (D)	7.4/11.4				X	X	X	X	X	X	X	X		
INC424 Dose Administration	6.1/7.4			X	X	X	X	X	X	X	X	X	X	

Evaluation	Reference to Section	Screening	Baseline	Day 1	Week 4 [#]	Week 8 [#]	Week 12 [#]	Week 24 [#]	Week 36	Week 48	Week 60 & q12w onwards	End of Study/End of Treatment Section 7.6.2	Follow-up / Study Completion Evaluation Section 7.6.3	
Visit name		1	2	3	4	5	6	7	8	9				
Day of visit		-28 to -1	-7 to -1	Day 1	Day 28	Day 56	Day 84	Day 168	Day 252	Day 336				
Record (D)														
Survival (D)	7.6.3.1													X
Leukemia-free survival (D)	11.6.1.1													X
Bone marrow biopsy (optional) including percentage blasts (D)	7.3/8.3.1.2													X

Table 7-2 Laboratory assessment schedule

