7.5 On treatment evaluations

On-treatment evaluations are scheduled for Study Visits at Day 1, and at the end of Weeks 4, 8, 12, and every 12 weeks thereafter. If it is determined at any Study Visit that the patient will discontinue study drug that day, then that study visit will be the End of Study Visit, and the End of Study Visit procedures will be followed.

After 4 weeks of treatment (Week 4 Visit), patients may have the dose of INC424 increased because of inadequate responses. At this visit or anytime during the study, the dose may be adjusted for safety, following the guidelines described in [Section 6.2](#), Dose Modifications. The individual study visit descriptions describe activities that must occur to support and document these dose changes.

This study schedule is designed to closely monitor any drug related adverse events associated with INC424. If, at any time during the study, a patient experiences unexpected signs or

symptoms, additional safety evaluations should be conducted at a regular Study Visit or unscheduled visit. For example, weekly monitoring is advised for patients with platelet counts < 100,000/ μ L or neutrophils < 1000/ μ L, and at least twice -weekly for platelets < 50,000/ μ L or neutrophils < 500/ μ L. Additionally, x-ray examination of the thorax, echocardiography, and pulmonary function testing and/or arterial blood gas analysis should be considered in patients developing new or worsening cardiopulmonary symptoms including cough, shortness of breath, exercise intolerance or peripheral edema.

Women of childbearing potential will be assessed for pregnancy status, either by serum or urine pregnancy tests, prior to starting treatment with INC424 only (see [Section 5.2](#)). If local requirements mandate more frequent testing, applicable sites will conduct monthly testing.

See [Section 6.2.2](#) and [Section 6.2.6](#) for criteria for mandatory reduction, interruption, or discontinuation of study drug based upon results of safety monitoring.

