7.5.1.11 Week 36 (\pm 7 days)

The following procedures will be performed and all observations will be recorded in the eCRF:

- Review of concomitant medications.
- Update transfusion history status.
- A complete physical examination will be performed, including body weight and measurement of spleen by palpation ([Section 8.2.3](#)).
- Vital signs (blood pressure, heart rate, respiratory rate and body temperature) to be performed in a sitting position after 5 minutes of rest.
- Blood sampling for serum chemistry tests, hematology, and optional coagulation (PT, PTT, or INR) (see [Appendix III](#)).
- Determination of ECOG performance status (see [Appendix IV](#)).
- MRU in the past month:
 - Number and duration of each hospitalization.
 - Number of emergency room visits.
 - Number of urgent care visits.
 - Number of additional general practitioner and specialist office visits.
 - Number of transfusions and transfusion dependency status.
 - Splenectomy or splenic irradiation.
- Drug accountability assessment (see [Section 6.5.4](#)).
- Record adverse events.
- Assess patient compliance.
- Document new (changed) OR ongoing dose information for INC424. Dose changes that are necessary between study visits will be communicated immediately and directly to the patient by telephone; the communication will be documented in the source documents.
- INC424 for the next 84 days (plus overage) will be dispensed along with dosing instructions.
- Patients will be instructed to call the investigator or designated research staff if they experience any unexpected and unfavorable signs and/or symptoms. Patients will be reminded to bring the study drug to the clinic with them.

7.5.1.12 Week 36 through Week 48

Patients will self-administer INC424 BID as instructed, morning and evening, in an outpatient setting. Patients will call the investigator or designated research staff if they experience any unexpected and unfavorable signs and/or symptoms.

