7.6.2 End of treatment evaluations

7.6.2.1 End of study or early termination visit

The End of Study or Early Termination Visit constitutes the final study visit where study drug has been taken. An End of Study Visit may occur with a planned discontinuation for any reason (e.g., at Week 20, it is determined that patient will participate in the study only 1 more month; therefore, the Week 24 Visit will become the End of Study Visit).

The following procedures will be performed and all observations will be recorded in the eCRF:

- Review of concomitant medications.
- Update transfusion history status.
- A targeted physical examination will be performed, including body weight and measurement of spleen by palpation ([Section 8.2.3](#)).
- Vital signs (blood pressure, heart rate, respiratory rate and body temperature) to be performed in a sitting position after 5 minutes of rest.
- Blood sampling for serum chemistry tests, hematology (see [Appendix III](#)).
- Determination of ECOG performance status (see [Appendix IV](#)).
- Drug accountability assessment (see [Section 6.5.4](#)).
- Record adverse events.
- Document the dose the patient was on at the time of study discontinuation.
- Patients will be asked to return to the clinic between 28 and 37 days later for a final Follow-up Visit.
- The sponsor (Novartis Pharmaceuticals) will be notified of the patient withdrawal.

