8.3.3 Resource utilization

Medical resource utilization will be captured at each visit out to 48 weeks. Data collection will include medical resources utilized since the last visit. MRU includes office visits (general practitioner and specialist visits), procedures/treatments, emergency room visits, urgent care visits, hospitalizations, transfusions, splenectomy, splenic radiation and changes in concomitant medications.

9 Safety monitoring and reporting

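### Recall for medical resource use at Weeks 24, 36 and 48 is stated in two incompatible ways, and SAP 3.6 reports totals without saying what period they cover

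*Protocol*

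**What the plan says.** Documenting medical resource utilisation (MRU) is a secondary objective. Protocol 3.3.4 defines the hospital endpoint as "Frequency and duration of hospitalization from Baseline up to week 48 of therapy", and the synopsis repeats it.

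On-treatment visits fall "at the end of Weeks 4, 8, 12, and every 12 weeks thereafter" (Protocol 7.5). The recall rules are:

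- Protocol 7.5.1.9 (Week 24) and 7.5.1.13 (Week 48): "Medical resource utilization in the past month".
- Protocol 7.5.1.11 (Week 36): "MRU in the past month".
- Protocol 8.3.3, which applies to every visit out to 48 weeks: "Data collection will include medical resources utilized since the last visit".

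At the end of treatment, Protocol 7.5 says that if a patient is found at a visit to be stopping that day, "then that study visit will be the End of Study Visit, and the End of Study Visit procedures will be followed". The procedure list in 7.6.2.1 contains no MRU item, and the MRU row of Table 7-1 has no mark under End of Treatment or Follow-up.

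SAP 3.6 summarises frequencies at the end of each quarter, and the overall number and duration of hospitalisations at the end of the study. It gives no recall window, no denominator and no rule for building a quarter figure. SAP 2.3 sets a month at 4 weeks and a quarter at 12 weeks. SAP Section 4, which lists changes to the protocol's analyses, covers only the transfusion definitions.

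**The concern.** At Weeks 4, 8 and 12 the two recall rules agree, because those visits are 4 weeks apart. From Week 24 each visit follows a 12-week gap, and a one-month question cannot also cover everything since the previous visit. Both rules stand in current text.

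If sites followed the visit sections, the totals planned in SAP 3.6 would be counts over part of the period but would read as counts over all of it. A reader of the tables could not tell. The quarter figures have a second ambiguity: they could be the value recorded at the quarter visit, or the sum of the visits falling in the quarter, and these behave differently under one-month recall.

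A separate gap arises at discontinuation. Because a stopping visit becomes an End of Study Visit with no MRU collection, the time since the last MRU visit is not scheduled to be asked about under either recall rule.

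**Working it through.** The plan states no coverage figure to reproduce, so this is direct day-counting.

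Inputs: visits at Weeks 4, 8, 12, 24, 36 and 48 (Protocol 7.5); windows of ±7 days (visit sections, SAP 2.3); month = 28 days and quarter = 84 days (SAP 2.3). A 31-day month is my sensitivity assumption.

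**One later interval, visit sections governing.** Days not asked about = gap − recall.

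- Nominal: 84 − 28 = 56; 56/84 = 67%.
- With ±7 days at both ends the gap runs from 70 to 98 days. Lowest share, 31-day month: (70 − 31)/70 = 56%. Highest share, 28-day month: (98 − 28)/98 = 71%.

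**Baseline to Week 48, all visits attended, nominal spacing.**

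- 28-day month: 3 × 56 = 168 of 336 days (50%).
- 31-day month: 3 × 53 = 159 of 336 days (47%).
- Week 24 collected under 3-month recall: 2 × 56 = 112 of 336 days (33%). The Amendment 3 summary records that the Week 24 recall was changed from three months to one, so this case may apply to some patients. The log is used only for that and is not itself an inconsistency.

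**Quarter figures, visit sections governing, 28-day month.**

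- Visits summed within quarters: Quarter 1 covers 3 × 28 = 84 of 84 days; Quarters 2 to 4 cover 28 of 84 each. At a constant rate of use the later counts would be a third of Quarter 1 from recall alone.
- Quarter-visit value only: every quarter covers 28 of 84 days. There is no artificial fall, but each figure covers about a third of its quarter.

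**Protocol 8.3.3 governing.** Coverage between attended MRU visits is complete, 336 of 336 days.

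**Stopping at a scheduled visit where no MRU is taken.**

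- Weeks 4, 8 or 12: the preceding 28 days have no MRU, under either rule.
- Weeks 24, 36 or 48: the preceding 84 days have no MRU, under either rule.
- Under the visit sections, 56 of those 84 days would have gone unasked anyway, so the added loss is 84 − 56 = 28 days. For a stop at Week 36 the total is 56 + 84 = 140 of 252 days (56%), against 112 of 252 (44%) had MRU been taken at that visit.
- Under 8.3.3, a stop at Week 36 loses 84 of 252 days (33%).

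**The case against.** The best reply is that the effect is unknown. The eCRF is not in the documents, and if it followed 8.3.3 there is no recall loss between visits. That stands: the contradiction is certain, the understatement is conditional.

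Some of the data also have a second source. Transfusion history is updated at every visit, including End of Treatment and Follow-up. Inpatient admissions are reportable as SAEs, though Protocol 9.2.1 exempts some admissions as well as disease progression. This narrows the exposure to emergency, urgent-care, general-practitioner and specialist visits, and to the number and duration of hospitalisations. It does not remove it.

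Timing matters too. Recruitment ended on 31 December 2014, so Week 48 visits would have finished around the end of 2015, and correcting the protocol may change little remaining collection. That supports putting the weight on the SAP.

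Four stronger readings are tempting but not supported:

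- A reader might infer that later quarters will be wrongly compared with the 3-month baseline count. Neither Protocol 11.6.4.1 nor SAP 3.6 plans that comparison for visits or hospitalisations.
- A reader might infer that every stop costs a further 84 days. That length applies only at Weeks 24, 36 and 48, and it overlaps the recall gap.
- A reader might infer that one-month recall was deliberate throughout. The amendment log shows intent for Week 24 only.
- A reader might infer that nothing at all is collected at a stopping visit. Protocol 8.3.3 asks for MRU at each visit to 48 weeks, and a site could read that as including it.

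**Conclusion.** Wrong as written. Two current recall rules conflict at three of the six on-treatment MRU visits, and the SAP neither resolves the conflict nor states a denominator.

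If the visit sections governed, the overall number and duration of hospitalisations understate the Baseline-to-Week-48 endpoint: half the period is not asked about for a patient attending every visit (47% with a 31-day month), or about a third where Week 24 used 3-month recall. If 8.3.3 governed, only time after the last MRU visit is lost.

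These are shares of time; they equal shares of use only if use is even, which is an assumption. A cohort-level figure would need retention data that the documents do not give. The documents also do not support saying that the loss occurred, only that one of the two stated rules produces it. The objective is descriptive, so no error rate or power is involved.

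**What to change.** 1. Confirm from the eCRF the recall used at each visit, and for Week 24 by protocol version.
2. Reconcile Protocol 7.5.1.9, 7.5.1.11 and 7.5.1.13 with 8.3.3 accordingly. If one month was used, also state that the endpoint in 3.3.4 and the synopsis is covered only for the recalled periods.
3. In SAP 3.6, state the recall window at each visit and whether a quarter figure is the quarter-visit value or a sum of visits.
4. Report events and hospital days per patient-time of recall, among patients with an MRU assessment.
5. Label the overall hospitalisation totals as covering the recalled periods to Week 48, and note that no MRU is scheduled at End of Treatment.

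Cost: one eCRF check; a correction to 8.3.3 with a note at the endpoint, or to three visit sections, depending on the answer; and a denominator and footnotes in the SAP 3.6 tables. No patient procedure changes. The downside is slightly more analysis work and totals that look less complete.

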7.5.1.11 Week 36 (\pm 7 days)

The following procedures will be performed and all observations will be recorded in the eCRF:

- Review of concomitant medications.
- Update transfusion history status.
- A complete physical examination will be performed, including body weight and measurement of spleen by palpation ([Section 8.2.3](#)).
- Vital signs (blood pressure, heart rate, respiratory rate and body temperature) to be performed in a sitting position after 5 minutes of rest.
- Blood sampling for serum chemistry tests, hematology, and optional coagulation (PT, PTT, or INR) (see [Appendix III](#)).
- Determination of ECOG performance status (see [Appendix IV](#)).
- MRU in the past month:
 - Number and duration of each hospitalization.
 - Number of emergency room visits.
 - Number of urgent care visits.
 - Number of additional general practitioner and specialist office visits.
 - Number of transfusions and transfusion dependency status.
 - Splenectomy or splenic irradiation.
- Drug accountability assessment (see [Section 6.5.4](#)).
- Record adverse events.
- Assess patient compliance.
- Document new (changed) OR ongoing dose information for INC424. Dose changes that are necessary between study visits will be communicated immediately and directly to the patient by telephone; the communication will be documented in the source documents.
- INC424 for the next 84 days (plus overage) will be dispensed along with dosing instructions.
- Patients will be instructed to call the investigator or designated research staff if they experience any unexpected and unfavorable signs and/or symptoms. Patients will be reminded to bring the study drug to the clinic with them.

7.5.1.12 Week 36 through Week 48

Patients will self-administer INC424 BID as instructed, morning and evening, in an outpatient setting. Patients will call the investigator or designated research staff if they experience any unexpected and unfavorable signs and/or symptoms.

7.5.1.13 Week 48 (\pm 7 days)

The following procedures will be performed and all observations will be recorded in the eCRF:

- Review of concomitant medications.
- Update transfusion history status.

- A complete physical examination will be performed, including body weight and measurement of spleen by palpation ([Section 8.2.3](#)).
- Vital signs (blood pressure, heart rate, respiratory rate and body temperature) to be performed in a sitting position after 5 minutes of rest.
- Blood sampling for serum chemistry tests, hematology, and optional coagulation (PT, PTT, or INR) (see [Appendix III](#)).
- 12-lead ECG performed in the recumbent position after 5 minutes of rest.
- Determination of ECOG performance status (see [Appendix IV](#)).
- Complete FACT-Lym version 4 ([Appendix VII](#)) and FACIT-Fatigue Subscale (prior to examination) ([Appendix VIII](#)).
- Medical resource utilization in the past month:
 - Number and duration of each hospitalization.
 - Number of emergency room visits.
 - Number of urgent care visits.
 - Number of additional general practitioner and specialist office visits.
 - Number of transfusions and transfusion dependency status.
 - Splenectomy or splenic irradiation.
- Drug accountability assessment (see [Section 6.5.4](#)).
- Assess patient compliance.
- Record adverse events.
- Document new (changed) *OR* ongoing dose information for INC424. Dose changes that are necessary between study visits will be communicated immediately and directly to the patient by telephone; the communication will be documented in the source documents.
- INC424 for the next 84 days (plus overage) will be dispensed along with dosing instructions.
- Patients will be instructed to call the investigator or designated research staff if they experience any unexpected and unfavorable signs and/or symptoms. Patients will be reminded to bring the study drug to the clinic with them.

